The **Daily Tracking Group** will be given the traditional prescription of tracking every day during the 8-week intervention. The **1 On/1 Off Tracking Group** will be asked to track every day for a week, then to take a week off, and so on throughout the 8 weeks. This group will then track on weeks 1, 3, 5, and 7 for a total of 4 weeks of tracking. Although this group will only be tracking at the most 50% of the time, our previous study found that tracking 40% of the time was the threshold needed to lose ≥5% of weight which is the lower end of the program weight loss goal (5-10%). The **2 On/1 Off Tracking Group** will be asked to track every day for 2 weeks, then to take 1 week off, and so on throughout the 8 weeks. This group will then track on weeks 1, 2, 4, 5, 7, and 8, for a total of 6 weeks of tracking. Although this group will only be tracking at the most 67% of the time, our previous study found that tracking 67% of the time was the

threshold needed to lose ≥10% of weight which is the high end of the program weight loss goal (5-10%).

All three groups will be asked to continue their schedule of tracking in the month following the 8-week intervention (i.e., 12 weeks). We will compare groups on weight loss at 8 weeks, total days of tracking over 8 weeks, % who adhered to their prescription during the 8 week program, % who tracked <50% of the time, % who tracked >67% of the time, tracking burden, tracking enjoyment, intentions to continue tracking past 8 weeks, number of days tracked in the subsequent month, and weight loss at 12 weeks. Findings will inform a fully powered clinical trial of tracking prescriptions during a full-length weight loss program (6 months in duration).

Provide a clear and succinct summary description of the background information that led to the plan for this project:

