Follow-ups/Assessments: The follow-ups/assessments will occur at the 9 and 12-week marks after the intervention has begun. At the 9-week mark (the week after the program ends), participants will receive a link to an online REDCap survey. This survey will be a repeat of some of the measures assessed at baseline (indicated in the measures table below) and questions to solicit participants' feedback. Then, at both the 9 and 12-week assessments, the participants will also weigh in. At the 12-week assessment, we will also collect their MFP diary entries, but that does not require the participant to do anything. Participants will be compensated (compensation explained in Payment/Course Credit to Participants section) for completing these assessments.

Adverse Events: Adverse events will be documented during the intervention and assessments. AE's will be formally assessed during the 9-week assessment by asking questions in the REDCap survey. During the intervention, AE's will be documented when a participant reports it to the

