weight loss counselor or posts it in the Facebook group. If it is reported during the intervention, the counselors will notify a research coordinator within 24 hours of learning of the event. The study team will then report it to the IRB (immediately or at the time of annual renewal depending on the AE). If participants gain 5% or more weight during the intervention, this will be treated as an adverse event. The participant will receive a phone call and/or email from a research coordinator, and they will be asked questions to figure out the cause of their weight gain. We will also assess Binge Eating Disorder (BED) at this time. If BED is present, we will treat it as a study-related AE. We will only assess BED once, even if there are multiple AEs for weight gain. Participants will not be removed from the intervention if they have 5% or more weight gain. If a participant is losing twice the weekly goal, which is 4 pounds of weight loss a week, consistently for 3 or more weeks in a row, then we will contact them to find out how they are accomplishing that and determine whether they are doing anything that is unsafe. If it is determined that they are losing weight in an unsafe manner, we will record that as an AE and the PI will have a discussion with them privately about healthy weight loss and how to do so in a safe manner moving forward. If after that conversation, they are still consistently losing 4 pounds of weight loss a week (for another 3 weeks or more in a row), we will remove them from the study and refer them to the National Eating Disorders Association helpline (https://www.nationaleatingdisorders.org/help-support/contact-helpline).

Measures: See table below.

Data Collected	List of Measures	Screening/	8-week	F/up	F/up	Method
		Baseline	Intervention	#1	#2	
Inclusion/Exclusion	Initial screening	Х				REDCap or
criteria	survey*					Qualtrics or
						BuildClinical
BMI	Height	X				REDCap
	Weight	X	X	Х	Χ	REDCap
Demographics	Marital status,	X				REDCap
	education,					
	race/ethnicity,					
	sexual orientation,					
	work status,					
	household income,					
	household					
	members*					
Nutrition Literacy	The Nutrition	X		Х		REDCap
	Literacy Assessment					
	Instrument (NLit) ²⁸					
History of Weight	Weight loss	X				REDCap
Loss	attempts*					

	Use of diet tracking* Use of diet tracking apps*					
Binge Eating	SCID Eating Disorder		X**	X**		REDCap
Disorder	Examination Questionnaire ³²					

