Depression	Patient Health Questionnaire (PHQ- 8 ³³)	Х				REDCap
Engagement	Facebook Engagement*		Х			Grytics into REDCap
Diet tracking	Data extraction*		Х		Х	MFP records
Diet Tracking	Difficulty*			Х		REDCap
Acceptability (0-10	Time Consuming*					
scales)	Helpfulness*					
Intervention	Burden*			Х		REDCap
Feedback	Contamination*					
Adverse Event Assessment	Adverse Events*			Х		

^{* =} investigator derived

The Nutrition Literacy Assessment Instrument: The NLit demonstrated both factor validity and reliability (0.97, CI = 0.96–0.98) as well as test-retest reliability (0.88, CI=0.85–0.90).²⁸

SCID Interview for BED: The SCID's severity scales demonstrated substantial internal consistency (all Cronbach's alphas >.80), test-retest reliability, concurrent, and predictive validity.³²

Patient Health Questionnaire (PHQ)-8: The PHQ-8 is an 8-question measure like PHQ-9 (with the omission of one question). The Cronbach's α for the PHQ-8 was 0.88 which demonstrates good reliability and a Spearman coefficient of 0.616 which demonstrates good convergent validity when compared to the PHQ-9.³³ Together, this data shows the PHQ-8 is as valuable as the PHQ-9.

Data Analysis

For all studies, specify the analytic techniques the researcher will use to answer the study questions. Indicate the statistical procedures (e.g., specific descriptive or inferential tests) that will be used and why the procedures are appropriate. For qualitative data, specify the proposed analytic approaches.

^{** =} as needed for AEs

Intervention prescription. We will report the % of participants meeting the prescription. % of participants who are high trackers (tracked >70% of the time), medium trackers (tracked 40-69% of the time), and low trackers (tracked <40% of the time).

Recruitment. We will report numbers and reasons for exclusion using a CONSORT diagram and we will compare recruitment sources by gender and race/ethnicity yields.

Retention. We will calculate retention as the proportion of participants who complete the follow-up assessments in each condition and report this information using a CONSORT diagram. Engagement. Number of Facebook reactions (e.g., like, care, wow, etc.), replies, posts, and polls per participant during the program.

Diet tracking prescription acceptability. We will report on the difficulty level, time consuming, and helpfulness of tracking prescription, as well as intentions to keep tracking in the next month.

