The data report for the 8-week intervention will be sent to the two safety officers once followups have been completed. Recruitment is monitored daily during the recruitment phase by the research coordinators and research assistants. All surveys are monitored once submitted to REDCap within 48 business hours by the research coordinators and research assistants. The Facebook group is monitored daily by the coaches. Weigh-in submissions are monitored weekly by the research coordinators and research assistants. App usage is monitored weekly by the research assistants, research coordinators, and the data managers. All data is continuously reviewed by the data managers.

2. Safety Monitoring Committee

The two safety officers for this project will include faculty independent from the research team with expertise in clinical psychology, exercise and weight loss interventions, and an understanding of the types and severity of injuries commonly experienced during weight loss trials. The two safety officers will review the reports sent by the PI/statistician and will use a checklist to document any corrective actions that should be communicated to the principal investigators, the University of Connecticut IRB, and the NIH. In addition, the safety officers may include documentation on whether the principal investigators should provide follow-up to a participant.

3. What data will be monitored:

Recruitment rates and adherence to inclusion/exclusion criteria, and ethnic diversity goals:

Recruitment progress, including baseline characteristics, will be reviewed. This review will ensure that project deadlines are being met, that participants meet eligibility criteria, and that the ethnic diversity goals outlined in the grant proposal are being met. Recruitment progress is monitored weekly, and a final report will be provided in the safety report.

Adherence to study protocols:

Quality control will be conducted in all phases of the project. The Facebook group will be monitored daily for intervention protocol adherence. A final report will be provided in the safety report.

Adverse events:

The adverse event report will include a listing of all adverse events including duration, severity, seriousness, relatedness, action taken, and resolution. Adverse events are documented throughout the intervention and at follow-up. A final AE report will be provided in the safety report. In the event of a serious adverse event, the safety officers will be notified immediately.

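### No adverse-event question is scheduled after week 9, and the 5% weight-gain rule is worded for the 8-week program, although assigned tracking and weigh-ins run to week 12

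*Protocol*

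**What the plan says.** **Assigned schedule.** Protocol, Purpose/Introduction: "All three groups will be asked to continue their schedule of tracking in the month following the 8-week intervention (i.e., 12 weeks". The same paragraph lists days tracked in that month and weight loss at 12 weeks among the outcomes on which the groups are compared.

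**Week-12 contact.** Design, Procedures, Materials and Methods, Follow-ups/Assessments: "Then, at both the 9 and 12-week assessments, the participants will also weigh in". Only the week-9 assessment has a survey. Tracking diaries are pulled at week 12 without any action by the participant. The Study Design paragraph, the participant-time table and the payment section all describe week 12 as a weigh-in only.

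**Adverse-event questions.** Adverse Events paragraph: "AE's will be formally assessed during the 9-week assessment by asking questions in the REDCap survey". In the measures table the row "Adverse Event Assessment" has one mark, at the first follow-up.

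**Weight gain and binge eating.** The same paragraph: "If participants gain 5% or more weight during the intervention, this will be treated as an adverse event". The contact that follows such a gain leads to: "We will also assess Binge Eating Disorder (BED) at this time". The table row that begins "SCID Eating Disorder" is marked, as needed for adverse events, at the 8-week intervention and the first follow-up. Its second follow-up cell is empty. Weight is marked at both follow-ups.

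**General statements.** The Adverse Events paragraph opens by saying that events are recorded in the program and at the assessments, in the plural. Data Safety Monitoring, item 3, says: "Adverse events are documented throughout the intervention and at follow-up". Item 5 requires deaths and serious events to be reported and states no time limit.

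**The concern.** The randomised element of this trial is the tracking prescription, and it does not end when the counselor-led program ends at week 8. The month after it counts as study time: the schedule continues, diaries are extracted and a weight is taken. The procedures that ask about harms, or that turn a weight into an adverse event, are tied to the 8-week program or the week-9 survey.

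Two things are at stake. First, the Potential Harms section names exercise injury and cardiovascular events as risks. Non-serious events of this kind after the week-9 survey would reach the record only if a participant volunteered them. Second, two participants with the same gain of 5% or more would be treated differently according to when it was seen. During the program it is an adverse event that leads to a contact and a binge-eating check. At week 12 the protocol does not say what it is.

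The safety officers receive their report, including the final adverse-event report, once follow-ups are complete. Its solicited content would stop at week 9. The pilot is meant to inform a full-length trial, so an uneven harms record would carry forward.

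**Working it through.** The protocol states no figure to reproduce. The check sets the passages side by side and adds simple arithmetic on the follow-up window.

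**Inputs**
- Assigned schedule ends: week 12 (Purpose/Introduction).
- Program ends: week 8 (Intervention).
- Last scheduled adverse-event question: week 9 (Adverse Events paragraph; measures table).
- Weight-gain rule: worded for the intervention, so to week 8 (Adverse Events paragraph).
- Last marked binge-eating assessment: first follow-up, week 9 (measures table).
- Last study weight: week 12 (Follow-ups/Assessments; measures table).
- Planned sample: 108.

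**Coverage by mechanism**

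| Mechanism | Last covered week | Weeks not covered | Share of 12 weeks |
|---|---|---|---|
| Adverse-event questions | 9 | 12 − 9 = 3 | 3/12 = 25% |
| Binge-eating check, as marked in the table | 9 | 12 − 9 = 3 | 3/12 = 25% |
| 5% gain rule, as worded | 8 | 12 − 8 = 4 | 4/12 = 33% |
| Weight measurement | 12 | 0 | 0% |
| Tracking diary data | 12 | 0 | 0% |

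The second and third rows do not quite agree with each other. The table allows a binge-eating assessment at week 9, while the rule that triggers it is worded for a program that ended at week 8. If the table mark is meant to bring the week-9 weight under the rule, the gap for the rule falls from 4 weeks to 3.

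**Do the arms still differ in the uncovered weeks?** The protocol lists tracking weeks only to week 8. Continuing each pattern is an assumption and gives, for weeks 9 to 12:
- Daily: weeks 9, 10, 11, 12, so 4 tracking weeks.
- 1 On/1 Off: weeks 9 and 11, so 2.
- 2 On/1 Off (weeks 1, 2, 4, 5, 7, 8, then 10, 11): 2.

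The prescriptions therefore still differ between daily tracking and the break arms.

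**How often would the gain rule matter at week 12?** This cannot be computed, because the reference weight for the 5% is not stated. Take a participant who has lost 5%, the lower program goal, by week 8 and stands at 95% of baseline:
- Reference is baseline: the threshold is 105% of baseline, a regain of (105 − 95)/95 = 10.5% of the week-8 weight in about four weeks.
- Reference is the week-8 weight: the threshold is 1.05 × 95 = 99.75% of baseline, so a return almost to the starting weight is enough.

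The number affected could be close to nil under the first reading and larger under the second.

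**General against specific text.** The two general statements promise documentation at the assessments and at follow-up. The specific procedures and the table provide a question at week 9 and none at week 12. Item 5 of Data Safety Monitoring promises assessment and follow-up to resolution for events arising in the intervention, and is likewise silent on the month after it.

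**The case against.** A reader might infer that harms in the last month go uncollected, that spontaneous reporting ends with the program, or that the plan stops looking. The documents support none of these. The Adverse Events paragraph and Data Safety Monitoring item 3 both say in general terms that events are documented beyond the program. Deaths and serious events must be reported with no time limit. Nothing says that the Facebook group closes or that staff would turn away a report made after week 8. Difficulty restarting after a break, which the Purpose section presents as a drawback of breaks, would show in the week-12 tracking data, and regain in the week-12 weight. Both are to be reported under Data Analysis.

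It can also be argued that one structured query just after the active program is a reasonable choice in a behavioral pilot whose protocol calls its risks minimal, with a week-12 visit kept deliberately light. The week-9 survey can also pick up events from the first week after the program, so the gap in questions is about three weeks and not a full month.

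These points narrow the concern and lower its weight. They do not remove it. No question, instrument or rule is scheduled at week 12, and the general statements name no procedure that would fill the gap. That regain would concentrate in weeks 9 to 12 is plausible, but the protocol gives no figure for it.

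**Conclusion.** The point holds as a gap in systematic solicitation and classification of harms. Adverse-event questions stop at week 9, leaving about 3 of the 12 prescribed weeks (25%) in which non-serious events are not asked about, for all 108 participants. The weight-gain rule as worded leaves about 4 of 12 weeks (33%) outside it, or about 3 if the table's week-9 binge-eating mark is taken to extend the rule. A gain of 5% or more first seen at week 12 would be in the weight data without any statement of whether it is an adverse event.

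This rests on two assumptions: that the specific procedures and the measures table govern what is done in practice, and that the intervention in the weight-gain rule means the 8-week program. The number of events that would be missed or left unclassified cannot be estimated from the protocol. The gap does not invalidate the pilot. It is worth closing because the missing step is small and the prescription under study is still in force.

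**What to change.** 1. Add the existing week-9 adverse-event questions to the week-12 contact, asking about events since the last survey.
2. Mark adverse-event assessment at the second follow-up in the measures table, and adjust the Follow-ups/Assessments text, the participant-time table and the payment section, which now describe a weigh-in only.
3. Reconcile the Adverse Events paragraph and the measures table with Data Safety Monitoring items 3 and 5 and with the continued schedule in Purpose/Introduction. The protocol should state which study weights the weight-gain rule and the binge-eating check cover, and the reference weight for the 5%. Which weights those should be is for the investigators to decide.

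The cost is a few more minutes per participant at a contact that is already scheduled and already paid ($25), plus some additional follow-up of reported events. If the investigators prefer to keep week 12 as a weigh-in only, the protocol and the final adverse-event report should say that solicited events run to week 9.
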